The partnered intervention consists of the following 4 evidence-based strategies: (1) written agreements of collaboration for dental screening at the site level; (2) culturally-tailored and language-specific adaptation of materials at the community and site levels; (3) demonstrations with role-playing of proper brushing with fluoride toothpaste and flossing techniques at the site and provider levels; and (4) community health worker (CHW) follow-up with patients about oral health care receipt and dental hygiene behaviors at the family and patient levels.

[figure not shown]
Patient Participants

Patient participants refer to study participants who are also patients screened at the urban outreach centers. Patient participants are first enrolled as EHR patient participants as part of the feasibility and acceptability study of this form of patient tracking. A subset of the EHR patient participants also complete exit interviews after the intervention at urban outreach centers and are referred to as interview patient participants.

Non-Patient
Participants

Non-patient participants refer to all other study participants who are not patients screened at the urban outreach centers, including community advisory board (CAB) members, research staff, New York University (NYU) administrators, providers (dentists and CHWs), and outreach site directors.

PROTOCOL SUMMARY

Title: Implementing a Participatory, Multi-level Intervention to Improve Asian American Health

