3.2 Study Outcome Measures

3.2.1 *Primary*

Patient satisfaction with the partnered intervention components, based on exit interviews.

3.2.2 *Secondary*

Table 1 reflects the series of secondary outcome measures associated with the objectives of the study (i.e., the feasibility and acceptability of the partnered intervention).

Table 1. List of secondary outcome measures, with their corresponding constructs, levels of analysis, and data sources.

--

Constructs	Levels of Analysis	Measures (Quantitative / Qualitative)	Data Sources
IMPLEMENTATION OUTCOME MEASURES			
Acceptability	Provider	satisfaction with the partnering components and perceived ease of use of the remote entry EHR	exit interviews with patients; semi-structured interviews
Adoption	Provider Institution	uptake and utilization of remote entry EHR and partnering components by providers and program	observation; semi-structured interviews; EHR
Costs	Institution	intervention and implementation costs, including investment, supply, and opportunity costs	semi-structured interviews; EHR
Feasibility	Provider Site	extent to which the remote EHR entry and partnered intervention model are compatible with resources and training	semi-structured interviews; EHR
Fidelity	Provider	adherence to program protocol and quality of delivery	CHW logs; self-report
Sustainability	Institution Site	sustained remote EHR use at outreach events and partnering package of interventions	semi-structured interviews; EHR
SERVICE OUTCOME MEASURES			
Equity	Community Provider Family Patient	support from community partners, providers (including NYU Dentistry), family members & patients to direct resources to less well-served and less well-studied populations (Chinese American adults)	baseline survey; follow-up patient interviews; semi-structured interviews; EHR
ORGANIZATIONAL CHARACTERISTICS			
Engagement	Institution Site	commitment, involvement & accountability of leaders with the implementation	semi-structured interviews

- Work flow analysis of the interviews of research staff, NYU administrators, and providers (dentists and CHWs) is a secondary measure designed to evaluate and refine the use of the remote EHR.

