12.4 Final Analysis Plan

Acceptability of the partnered intervention will be assessed through exit interviews of the interview patient participants.

As we did with the Sikh American project, we will utilize a pre-post retrospective evaluation design. In this format, all questions will be asked in a single exit interview, but where applicable, will use the phrasing, "Prior to the beginning of the program..." followed by, "At the present time..." Table 3 lists the questions/domains we will use, and expected % changes we hypothesize we will observe in the current study. The percent change from pre-post will be compared using t-tests for proportions. Given that many of the answer choices are non-binary, we will also compare the shift of responses from pre-post across the categories of response using chi-squared tests. Note that this is not an exhaustive list of questions that will be asked; we are simply highlighting those questions that we will use to quantify acceptability. The full planned questionnaire is attached.

Health care utilization and oral health promotion measures: Our ultimate health care utilization measure of interest is receipt of a dental visit within the last 12 months. This will be measured using the Medical Expenditure Panel Survey (MEPS) definition, where dental visit refers to care by or visits to any type of dental provider. This will allow for

direct comparison with Healthy People 2020 Leading Health Indicator OH-7 to increase the proportion of children, adolescents, and adults who used the oral health care system in the past year.

Our central oral health promotion measure is self-reported brushing of teeth for 2 minutes twice a day with a soft-bristled toothbrush and fluoride toothpaste at the interview patient participant's 1 month follow-up visit. For the primary health care utilization measure of receipt of a dental visit within the last 12 months, we will also access the NYU Dentistry EHR database and follow-up with oral health care providers identified by participants in HIPAA approved procedures to ascertain receipt of a dental visit in the last 12 months.

Table 3 provides the measures and definitions of the oral health promotion, self-efficacy, and acceptability measures used in our prior research with the Sikh American community that will be adapted for the present F & A study with the Chinese American community.

Table 3. Measures and definitions of oral health promotion, self-efficacy, and acceptability measures

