Question/Domain	Observed Change in Sikh American Project	Expected Absolute Percent Change	Expected Relative Percent Change*
How often do you brush your teeth for at least two minutes?	Increase from 17.9% to 64.7% of those reporting "More than once a day"	+45%	+261%
How often do you floss?	Increase from 4.4% to 22.1% of those reporting "More than once a day"	+20%	+400%
How confident... a) are you that you know how to take good care of your mouth, teeth, and gums? b) do you feel asking your dentist or oral hygienist questions?	a) Increase from 0% to 65.7% of those reporting "Very confident" b) Increase from 7.4% to 75% of those reporting "Very confident"	a) +65% b) +65%	a) +6500% b) +864%
Agreement with the following statements: a) CHW answered my concerns and questions b) CHW helped me to improve how I take care of my health c) Information and topics were informative d) In-person demonstrations helpful in improving oral health	Reported "Strongly Agree" a) 57.4% b) 60.3% c) 69.1% d) 76.1%	N/A	N/A

**We additionally list relative percent change in the case that baseline behaviors among the Chinese American community are very different from the Sikh American community.*

The threshold for success for acceptability of the partnered intervention will be that 80% or more of interview patient participants rate all 4 acceptability questions as agree or strongly agree.

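### The 80% acceptability rule counts no patient rating of the adapted materials' language and cultural fit or of the dental screening, so meeting it does not establish satisfaction with the intervention components

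*Combined protocol and SAP*

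**What the plan says.** The primary outcome in section 3.2.1 is "Patient satisfaction with the partnered intervention components, based on exit interviews". Special Terms lists four components: site-level written agreements covering dental screening; "culturally-tailored and language-specific adaptation of materials at the community and site levels"; demonstrations with role-play; and CHW follow-up.

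The success rule stands below Table 3 in section 12.4: "80% or more of interview patient participants rate all 4 acceptability questions as agree or strongly agree". The four statements are "a) CHW answered my concerns and questions b) CHW helped me to improve how I take care of my health" and "c) Information and topics were informative d) In-person demonstrations helpful in improving oral health".

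On the role of the listed questions, section 12.4 says "Note that this is not an exhaustive list of questions that will be asked" and that "we are simply highlighting those questions that we will use to quantify acceptability". It adds "The full planned questionnaire is attached"; that questionnaire is not in the text available for this review.

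Section 7.2 has a dentist examine each patient and go over the findings, and has CHWs give out the customized literature; it also places the exit interview among the outreach center activities. Section 7.3 puts CHW follow-up at approximately one month after the intervention. Section 12.2 states an 80% bar in other terms: satisfied or very satisfied with the components, among enrolled patient participants.

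**The concern.** The outcome is worded for the components as a set, but the rule that decides it draws on a narrower group of statements. The materials were adapted specifically for this community. Section 6.1 gives that work a multi-step process with the community advisory board (CAB), section 2.3.2 names the translated literature in the expected benefit, and section 15.4 gives cultural and linguistic relevance of the materials as a reason for enrolling only people of Chinese ethnicity.

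If patients find the topics useful but the literature poorly suited to them, the rule as written does not register it. A pass would still be read, in the words of the primary outcome, as satisfaction with the components, and would inform the design of the larger randomized trial that section 3 names as the ultimate goal.

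**Working it through.** **1. Reproduce the denominator and the bar.** Section 5.1 gives 30 patients at each of 3 centers and about 60% of 150. These agree: 3 × 30 = 90 and 0.60 × 150 = 90. The bar in patients is 0.80 × 90 = 72. Section 12.2 reports no formal sample size estimate, so there is no power figure to reproduce.

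**2. Set elements beside items.**

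| Element | Reaches the patient before exit? | Counted by the 4-item rule? |
|---|---|---|
| Component 1: written agreements | No, site level | No |
| Dental screening and results review (an activity at the event, not itself a listed component) | Yes (7.2) | No |
| Component 2: adapted materials | Yes, as literature (7.2) | Content partly, through item c; language and cultural fit, no |
| Component 3: demonstrations | Yes | Yes, item d |
| CHW's help and answers | Yes | Yes, items a and b |
| Component 4: CHW follow-up | No, about 1 month later (7.3) | Cannot be |

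Items naming the screening: 0 of 4. Items naming language or cultural fit: 0 of 4.

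**3. Consequence for the rule.** Let A be the number of patients who agree or strongly agree on all four items. Success is A ≥ 72. A rating of the materials' fit, or of the screening, appears nowhere in A. With A = 72, the number of patients content with either could be anything from 0 to 90 and the verdict would be the same.

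**4. What added items do to the chance of success.** The documents give no agree-or-strongly-agree rates; the prior-project figures in Table 3 (57.4% to 76.1%) are for the top category only. The rates below are therefore assumptions. If q is the true share meeting a criterion, and patients respond independently, the chance of reaching the bar is P(X ≥ 72), with X ~ Binomial(90, q).

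For a joint rule with one extra item, q = (true all-four share) × (share of those patients who also endorse the extra item).

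| True all-four share | Endorse extra item | q | Chance of at least 72 of 90 |
|---|---|---|---|
| 85% | no extra item | 0.850 | 92.6% |
| 85% | 95% | 0.8075 | 63.3% |
| 85% | 90% | 0.765 | 25.9% |
| 85% | 80% | 0.680 | 0.8% |
| 90% | no extra item | 0.900 | 99.9% |
| 90% | 95% | 0.855 | 94.3% |
| 90% | 90% | 0.810 | 65.5% |
| 90% | 80% | 0.720 | 5.4% |

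The last two columns also serve for a bar applied to one item alone. An item with 85% true agreement passes with probability 92.6%, one with 72% with probability 5.4%. A separate bar therefore shows which element fell short, whereas a joint bar mixes them and becomes much harder to meet.

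**5. The two wordings of the bar.** Section 12.2 uses a satisfaction scale and enrolled patient participants; section 12.4 uses an agreement scale, four items and interview patient participants. If the section 12.2 denominator means all 150 patient participants, the bar is 0.80 × 150 = 120, more than the 90 who give an exit interview (90/150 = 60%). That reading cannot be met, so the intended denominator has to be stated.

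**The case against.** A reader might infer that no patient is asked about the materials or the screening at all. The documents do not support that. Section 12.4 says the list is not complete and that the full questionnaire is attached; section 7.2 lets the CAB and staff adapt the survey before use; and section 8.1.3 contains an overall 1–10 rating and a question on screening length. That section opens with non-patient interviews but does not clearly say who answers its acceptability questions. This part of the objection stands. However, none of those questions enters a rule that is fixed at four items.

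Item c can take in the content of the literature, and items c and d rate a program that section 7.2 itself describes as tailored. That also stands, as partial cover: informative is not the same as suited to one's language and culture.

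The screening is not a listed component. It enters only through a site-level agreement, so the gap on materials is the stronger half of the point.

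Cultural fit is also examined elsewhere: CAB review of the adapted materials (6.1), pilot testing of the curriculum (6.2) and a materials review in non-patient interviews before implementation (Table 2). These steps reduce the risk of poorly fitting materials, but they do not supply the patient exit ratings on which the primary outcome is defined.

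Finally, the section 12.2 bar is worded for the components and so matches the primary outcome better. But section 12.2 ties it to no items, and it sits unreconciled beside section 12.4.

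**Conclusion.** The point holds as a mismatch between the primary outcome and the rule that decides it. The rule counts no rating of the materials' language and cultural fit, none of the screening, and cannot cover CHW follow-up. Reaching 72 of 90 supports acceptability of the CHW, information and demonstration elements, and not of the components as a set.

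The mismatch rests on item wording and needs no assumed rate. The probabilities in the working do rest on assumed agreement rates and independent patients; they show only how a change of rule would behave. Nothing in the documents indicates that patients will in fact be dissatisfied with the materials or the screening.

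This should be fixed before the exit survey is final. It is not fatal: the study is an unsized feasibility study, section 12.3 plans interim reviews of interview data in order to modify the intervention, and the survey is still open to adaptation.

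**What to change.** - In Table 3 and section 12.4, add one exit statement, on the same agreement scale, on whether the materials suited the patient's language and culture. Optionally add one on the screening and results review, labelled as a patient-facing element and not as a listed component.
- Apply the 80% bar separately to each patient-facing element delivered by exit, and say which item or items represent each one.
- State that site-level agreements and CHW follow-up are not rated at exit.
- Alternatively, leave the four items alone and narrow the success claim to the CHW, information and demonstration elements.
- In either case keep one bar: reconcile sections 12.2 and 12.4 on scale, items and denominator.

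The cost is one or two more questions in a survey not yet final, some added text, and a bar that is harder to meet. If the joint all-items rule is kept, the loss can be large: in the assumed case of an 85% all-four share, one extra item endorsed by 90% of those patients takes the chance of success from 92.6% to 25.9%. The separate bar avoids compounding items in this way, but the study team should decide in advance what it will report if some elements pass and others do not.

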13 SOURCE DOCUMENTS AND ACCESS TO SOURCE DATA/DOCUMENTS

Study staff will maintain appropriate research records for this study, in compliance with ICH E6, Section 4.9 and regulatory and institutional requirements for the protection of confidentiality of subjects. Study staff will permit authorized representatives of NIDCR to examine (and when required by applicable law, to copy) research records for the purposes of quality assurance reviews, audits, and evaluation of the study safety, progress and data validity.

Patient participant data will be remotely entered directly into the EHR.

14 QUALITY CONTROL AND QUALITY ASSURANCE

The MPIs will be responsible for ensuring that the study is conducted according to the protocol and ensuring data integrity. The MPIs will review the data for safety concerns and data trends at regular intervals, and will promptly report to the IRB and NIDCR any Unanticipated Problem (UP), protocol deviation, or any other significant event that arises during the conduct of the study.

15 ETHICS/PROTECTION OF HUMAN SUBJECTS

15.1 Ethical Standard

The MPIs will ensure that this study is conducted in full conformity with the principles set forth in The Belmont Report: Ethical Principles and Guidelines for the Protection of Human Subjects of Research, as drafted by the US National Commission for the Protection of Human Subjects of Biomedical and Behavioral Research (April 18, 1979) and codified in 45 CFR Part 46 and/or the ICH E6.

15.2 Institutional Review Board

The protocol, informed consent form(s), recruitment materials, and all patient participant and non-patient participant materials will be submitted to the IRB for review and approval. Approval of both the protocol and the consent form must be obtained before any patient participant or non-patient participant is enrolled. Any amendment to the protocol will require review and approval by the IRB before the changes are implemented in the study.

15.3 Informed Consent Process

Informed consent is a process that is initiated prior to the individual agreeing to participate in the study and continues throughout study participation. Extensive discussion of risks and possible benefits of study participation will be provided to patient participants and their families, if applicable. A consent form describing in detail the study procedures and risks will be given to the patient participant in English or Mandarin Chinese (primary dialect of participating community sites). Consent forms will be IRB-approved, and the patient participant is required to read and review the document or have the document read to him or her. The investigator or designee will explain the research study to the patient participant and answer any questions that may arise. The patient participant will sign the informed consent document prior to any study-related assessments or procedures. Patient participants will be given the opportunity to discuss the study with their surrogates or think about it prior to agreeing to participate. They may withdraw consent at any time throughout the course of the study. A copy of the signed informed consent document will be given to patient participant for their records. The rights and welfare of the patient participants will be protected by emphasizing to them that the quality of their clinical care will not be adversely affected if they decline to participate in this study.

The consent process will be documented in the clinical or research record.

Consent for non-patient participant interviews for the knowledge modeling will take place where the interview happens, verbally over the telephone. [name], the Principal Investigator of the modeling site, will send the consent information sheet by e-mail when scheduling the interview, which will be at least 2 days in advance of the interview. To ensuring ongoing consent for follow-up interviews, [name] will remind

the non-patient participants about their previous consent and will resend the consent document if needed. [name] will obtain verbal consent for any subsequent recording of information collected during follow-up interviews. [name] will send the consent document ahead of time. Before recording, [name] will ask: Have you reviewed the information? Do you have any questions? If the non-patient participant answers “yes” to the first question and “no” to the second question, then she will ask: Is it OK if we start the interview now? and if taping the telephone call: Is it OK if I begin audio recording? After the participant answers “yes,” the interview will begin.

15.4 Exclusion of Women, Minorities, and Children (Special Populations)

The proposed study will enroll Chinese adults aged 21 years and older. No children will be included since there are separate and targeted NYU Dentistry programs for this age group. The study population is Chinese American adults living in any of the 5 boroughs of New York, NY. We estimate that approximately 60% of our enrolled patient participants will be women, based on our experience with conducting community-based screening events. All enrolled patient participants will be of self-reported Chinese ethnicity, to ensure that our partnerships and materials are culturally and linguistically relevant. Study sites will be concentrated in lower Manhattan (Chinatown and the Lower East Side) and the Sunset Park area of Brooklyn, which include dense ethnic enclaves of Chinese Americans.

15.5 Subject Confidentiality

Subject confidentiality is strictly held in trust by the investigators, study staff, and the sponsor(s) and their agents. This confidentiality is extended to cover testing of biological samples and genetic tests in addition to any study information relating to subjects.

The study protocol, documentation, data, and all other information generated will be held in strict confidence. No information concerning the study or the data will be released to any unauthorized third party without prior written approval of the sponsor.

The study monitor or other authorized representatives of the sponsor may inspect all study documents and records required to be maintained by the investigator, including but not limited to, medical records (office, clinic, or hospital) for the study subjects. The clinical study site will permit access to such records.

Certificate of Confidentiality

To further protect the privacy of study participants, the Secretary, Health and Human Services (HHS), has issued a Certificate of Confidentiality (CoC) to all researchers engaged in biomedical, behavioral, clinical or other human subjects research funded wholly or in part by the federal government. Recipients of NIH-funded human subjects research are required to protect identifiable research information from forced disclosure

per the terms of the NIH Policy (see <https://humansubjects.nih.gov/coc/index>). As set forth in 45 CFR Part 75.303(a) and NIHGPS Chapter 8.3, recipients conducting NIH-supported research covered by this Policy are required to establish and maintain effective internal controls (e.g., policies and procedures) that provide reasonable assurance that the award is managed in compliance with Federal statutes, regulations, and the terms and conditions of award. It is the NIH policy that investigators and others who have access to research records will not disclose identifying information except when the participant consents or in certain instances when federal, state, or local law or regulation requires disclosure. NIH expects investigators to inform research participants of the protections and the limits to protections provided by a Certificate issued by this Policy.

